
A.2. Clinical Trial Design Details

We will utilize the MOST procedure to assess the app suite specialty features’ efficacy and other performance aspects. MOST is explicitly designed to disentangle the effects of multiple components that make up an intervention^{26,105}—a key project goal given our intent to appraise the merit of novel, previously untested app features. Traditionally, multi-component interventions are subjected to efficacy pilot tests followed by large RCTs, but in the absence of systematic evaluations of singular components. However, in such cases: (a) the intervention may contain inert ingredients that contribute to subpar or cost-inefficient results; or (b) difficulties may arise in determining which intervention aspects contribute to efficacy, due to the presence of multiple components which have not been individually tested. In contrast, following

[figure not shown]

Figure 2. Theoretical Framework for the PA-tracking App Suite. SCT=Social Cognitive Theory; SET=Stereotype Embodiment Theory; PA=Physical activity; SA=Sedentary Activity

systematic optimization as facilitated by MOST, subsequent RCTs are expected to produce sharper, more interpretable results.

Based on recommendations from the MOST literature, we will employ a 2x2x2 factorial experiment in which three between-subject factors, corresponding to the presence vs. absence of each specialty feature, will be manipulated in a completely crossed design, given each participant's utilization of the core app. Following random assignment (using a computer algorithm designed for this purpose) to the eight conditions, participants will undergo a four-month intervention interval. Experimental outcomes will consist of pre-to-post change scores on PA-related and mediating variables, and documentation will also be provided for parameters such as usage frequency and user satisfaction that are pertinent to subsequent efforts to achieve optimization.

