Prospective participants who have been referred to the study team by FPCIW or who have responded to advertisements or presentations will be initially screened for eligibility over the phone or in person by authorized research personnel. After initial screening, informed consent materials will be sent or handed to prospective participants for pre-review. Authorized research personnel will then perform the consent process for qualifying participants at local community venues that are convenient to the participants. If an in-person meeting for enrollment (including consenting) is not feasible, we will conduct enrollment activities virtually through phone calls or videoconferencing, and will send consent forms electronically to participants using DocuSign or a REDCap eConsent form to review and complete. Only key personnel who are HIPAA and CITI certified, trained in consenting procedures, and do not have a conflict of interest will conduct the consent process. The consenter will explain the study procedures and describe in detail what will be expected of participants. Participants will have ample time to ask questions about the study and their role in it. If the individual is interested in participating, they will sign the consent form. If participants are not comfortable with the study, they may choose not to participate. Following consent, an assessment battery would be held next.

C. Procedures & Measurement

Participants will complete an orientation, either in-person or online, that includes activation of and training to use select app features on their personal phones. They will be encouraged to carry their phones during activity, a behavior we will reinforce by providing toting accessories (e.g., waist pouch) and monthly telephone check-ins beginning in week one. Participants will be shown how to manually enter PA data that cannot be captured automatically (e.g., due to water-based sports). During check-ins, participants will be offered technology support, and will be questioned about events that may have altered their phone usage or activity patterns (e.g., hospitalization). Additionally, a troubleshooting asynchronous hotline will be made available to participants during the intervention.

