Our biostatistician will secure and archive data, and will oversee all data analytic functions. Usage data for each participant will be obtained from storage within the app and downloaded manually at in-person assessment sessions. Data will be transferred to the biostatistician for analysis and storage on the USC secure network. activPAL data will be downloaded and cleaned. Using proprietary algorithms supplied by PAL Technologies, waking-hour wear periods will be identified for use in analysis.

Data analysis will be organized around the goal of providing multiple sources of information useful for future efforts to optimize the Moving Up app suite. We will calculate *descriptive statistics* at baseline and/or post-intervention for demographic, *app usage behavior* [proportion of days opening the app ≥ 1 time], *user satisfaction* [perceived app quality, physical activity-related (*objective physical activity* [primary outcome; daily steps], *sedentary activity time* [daily sitting time], *self-reported physical activity*, *functional mobility* [gait speed]), and mediational (i.e., *self-efficacy for physical activity*, *self-regulation for physical activity*, *family social support for physical activity*, *outcome expectation for physical activity*, *aging self-perceptions*, *views of aging*) outcome variables, both for the overall sample and by on/off status of each of three specialty features (i.e., Proof Positive, Coach Me, and On Your Feet).

Indicator variables will be created to code whether or not the participant had each of the specialty features installed on their phone as part of the intervention. Results regarding outcomes and hypothesized mediators will be calculated overall and by feature subgroup. The feature subgroups are not mutually exclusive since a participant can be randomized to receive 0, 1, 2, or all 3 of the features.

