Specialty feature condition effects on the *objective physical activity* (change in daily steps) primary outcome will be analyzed using a mixed effects linear regression model adjusted for confounders (including presence/absence of other specialty features, between-feature interactions, select demographic variables [age, sex, race/ethnicity, education]), and baseline daily steps. Although significance testing will provide merely one source of information in driving app optimization decisions, the anticipated sample size (N=90) was chosen to enable 80% power (given $\alpha=.10$ and a one-tailed test, as consistent with recommendations for pilot studies employing MOST) in testing experimentally based pre-post physical activity increases associated with a specialty feature (given an effect size of .45, a feasible value based on prior tests of technology-based physical activity intervention components). Using change-from-baseline scores for *objective physical activity*, we will derive Cohen's *d* effect sizes stratified by presence vs. absence of each specialty feature. For secondary physical activity-related outcomes and proposed mediators, we will conduct multiple one-tailed t-tests ($\alpha=.10$) to further explore the potential viability of the specialty features. To facilitate later RCT planning, we will also calculate single group pre-post change effect sizes for the full sample. Correlation coefficients will be calculated to assess associations between the primary outcome (change in daily steps) and proposed mediators. To analyze *app usage behavior* and *user satisfaction*, for each intervention feature considered separately, we will perform one-tailed t-tests to examine mean differences in each variable based on whether or not the participant was assigned to receive that feature.

After participants conclude the clinical trial phase, they will take part in an interview about their experience. Interview responses will be audio-recorded, transcribed verbatim, coded, and analyzed using qualitative data analysis software. All qualitative data analyses will be performed by the PI, Co-investigators, and/or authorized Research Assistants. Initial thematic analysis will incorporate codes suggested from the Health-ITUDEM.[71] Additional codes will be identified as they arise in the data. Rigor will be achieved through peer review of themes and by maintaining an audit trail of analytic memos.

IV. Protection of Human Subjects

A. Risks to Human Subjects

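### The feature indicators are defined by installation on the phone while neighbouring text refers to randomised assignment, and no analyse-as-randomised rule settles which applies

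*Combined protocol and SAP*

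**What the plan says.** All the relevant analysis wording is in Section III (Data Management, Analysis, & Statistical Considerations) of the combined protocol and SAP.

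- **Definition of the indicators.** They are created to "code whether or not the participant had each of the specialty features installed on their phone as part of the intervention". The next sentence has outcome and mediator results calculated overall and by feature subgroup.
- **Same paragraph, closing sentence.** "The feature subgroups are not mutually exclusive since a participant can be randomized to receive 0, 1, 2, or all 3 of the features".
- **Primary model.** It estimates "Specialty feature condition effects on the *objective physical activity* (change in daily steps) primary outcome", adjusting for the other features, between-feature interactions, four demographic variables and baseline steps.
- **Standardised effects.** Cohen's d values are "effect sizes stratified by presence vs. absence of each specialty feature".
- **Usage and satisfaction.** Mean differences are tested "based on whether or not the participant was assigned to receive that feature".

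On design, Section II.A.2 describes a 2x2x2 factorial: "Following random assignment (using a computer algorithm designed for this purpose) to the eight conditions", participants enter the four-month intervention. Section II.C says that orientation, in person or online, "includes activation of and training to use select app features on their personal phones".

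The plan has no intention-to-treat or analyse-as-randomised sentence. It does not say how to code an assigned feature that was not installed, or an unassigned feature that was installed by mistake.

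**The concern.** Installation comes after randomisation. Where it differs from assignment, grouping by installation is an as-treated comparison. Someone randomised to have a feature, but on whose phone it could not be activated, would leave the feature-present group and join the feature-absent group. If such people also tend to change their steps less, perhaps because of technical skill or health, the move raises the mean of one group and lowers the mean of the other. Both shifts favour the feature.

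The same person would still count as assigned in the usage and satisfaction tests, so results for one feature would rest on two different groupings.

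This matters even though the trial is a pilot. Section II.A.2 plays down significance testing and relies on effect sizes, among other information, to select and refine components. A distorted effect size would feed directly into that decision. The same section rests its case for adequate numbers on a 45 vs 45 comparison per feature, created by randomisation.

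**Working it through.** **1. The plan's own figure.** Inputs from Section III and Section II.A.2: 45 per group, effect size 0.45, one-tailed alpha 0.10.

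- Standard error in SD units: √(1/45 + 1/45) = 0.2108.
- Power = Φ(0.45/0.2108 − 1.2816) = Φ(0.853) = 80.3%. The noncentral t gives 80.0%.

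The stated 80% reproduces, so the power calculation is not at issue.

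**2. The labels side by side.** The single sentence that defines the indicators uses installation. The sentence on overlapping subgroups uses randomisation. The primary model speaks of condition effects and Cohen's d of presence vs absence, neither tied explicitly to one or the other in Section III. Only the usage and satisfaction tests are explicitly by assignment. For steps, secondary outcomes and mediators, the installation definition therefore applies by default.

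**3. What the literal coding could do.** The following are assumptions, because the documents give no figure for any of them:

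- there is no true feature effect;
- k of the 45 assigned a feature do not get it installed, and the 45 not assigned contain the same share of would-be non-installers;
- non-installers' mean step change is s SD worse than that of the others, with s = 0.5;
- no covariate adjustment is made, and the within-group SD is 1.

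Set the installers' mean to 0. The as-installed present group then has mean 0 and size 45 − k. The as-installed absent group has size 45 + k and mean

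[45 × (−(k/45)s) + k × (−s)] / (45 + k) = −2ks/(45 + k).

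The spurious benefit is therefore 2ks/(45 + k). Its rejection probability is approximately Φ(benefit/√(1/(45−k) + 1/(45+k)) − 1.2816).

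| k of 45 | Groups | Spurious benefit (SD) | False-positive rate (nominal 0.10) |
|---|---|---|---|
| 2 | 43 vs 47 | 2/47 = 0.043 | Φ(0.202 − 1.282) = 0.14 |
| 5 | 40 vs 50 | 5/50 = 0.10 | Φ(0.471 − 1.282) = 0.21 |
| 9 | 36 vs 54 | 9/54 = 0.167 | Φ(0.775 − 1.282) = 0.31 |

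At k = 5 the benefit is 0.10/0.45 = 22% of the planned effect.

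**4. Sensitivity to the assumed deficit.** At 10% non-installation, the false-positive rate is 10% when s = 0, 19.7% when s = 0.5 and 33.6% when s = 1. As-randomised coding stays at 10% in every case. With k = 0 the two codings are identical.

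**5. Price of as-randomised coding.** Suppose a share f is not installed and the 0.45 effect occurs only in installers. The as-randomised contrast is then 0.45(1 − f):

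- f = 5%: 0.4275, power 77.2%;
- f = 10%: 0.405, power 73.9%;
- f = 20%: 0.36, power 66.5%.

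**The case against.** The strongest reply is that the plan as a whole means assignment, and that *installed* is one loose word. The defining sentence limits installation to what was done as part of the intervention, and the intervention is what was allocated. The paragraph closes by referring to randomisation. Elsewhere the document uses *conditions* for the eight randomised arms, and Section II.A.2 defines the three experimental factors as presence vs absence of each feature. On this view, condition effects and presence vs absence in Section III already point to assignment. Much of this stands: the authors may well equate installed with allocated. A reader might infer that the plan deliberately adopts an as-treated analysis, or that the randomised comparison is already lost. The documents do not support either inference.

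Two routes into the wrong group that a reader might also infer do not work. Use of the features is voluntary (Section IV.A, Overall burden), but non-use does not change whether a feature was installed. Nor does a change of phone undo the fact that the participant had it. Refusal to have a feature installed is not described anywhere. Failed activation is the main route left, and the plan limits it: eligibility requires observed ability to operate a smartphone at orientation, and monthly technology support and a hotline are provided.

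The scenario inputs have no source in the documents. The calculation also assumes that non-installers remain among the 90 completers, and it leaves out the planned covariate adjustment. These objections limit the size of the problem. They do not remove the inconsistency, because nothing tells an analyst to set the installation definition aside.

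**Conclusion.** The supportable finding is inconsistent wording combined with a missing rule. The one sentence that defines the indicators uses a post-assignment event, nearby text uses assignment, and the plan does not say which governs steps, secondary outcomes and mediators.

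Harm requires three things together: the definition is followed literally, some assigned features are not installed, and non-installation is related to step change. The documents make the first possible and give no rate or prognosis for the other two. The 0.04 to 0.17 SD range is therefore an illustration resting on an assumed 0.5 SD deficit, not an estimate for this trial. If all features are installed, or non-installation is unrelated to outcome, the spurious benefit is zero.

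Confidence is moderate. This is a cheap improvement rather than a demonstrated error in the randomised comparison.

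**What to change.** In Section III, replace the installation wording so that each feature indicator, and each interaction built from it, is coded from the randomised assignment whatever was later installed, removed or used. Apply this to the primary model, Cohen's d, secondary outcomes and mediators, matching the rule already used for usage and satisfaction. Add one sentence stating that participants are analysed as randomised.

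Record actual installation separately and report it by assigned group, including any unassigned feature installed in error. Label any as-installed analysis as a sensitivity analysis.

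The cost is a few lines of text and an installation record; the assignments are already held. The statistical downside is dilution when assigned features are not installed: power of about 74% rather than 80% at 10% non-installation, if the effect occurs only in installers. With full installation, the results do not change.

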Each specialty feature will be provided to half of the participants, leading to respective comparative assessments that involve 45 vs. 45 (feature present vs. absent) participants. Accordingly, it is incorrect to conceptualize this design as a test of outcome differences between eight separate inadequately powered cells; rather, the intent is to collapse information across cells so as to obtain a reasonably large sample size when examining each component's performance.[24] Further, because the specialty features would be inexpensive to download if used in large-scale distributions of the app, and because they have been carefully designed to reflect empirically supported theory, it is important to avoid premature elimination of features on the basis of non-significant experimental effects which in actuality may stem from sample size limitations. Consequently, in evaluating intervention components we will downplay the importance of (though still include) significance testing of PA outcomes, and instead will incorporate the total array of relevant information (e.g., effect sizes, usage rates, satisfaction ratings) in the final component selection and fine-tuning process.

B. Participants, Recruitment, and Consent

For Aim 1, a convenience sample of 15 elders will be recruited from independent-living communities within FPCIW's 2,000-member senior network in Los Angeles (LA) and local senior venues. An estimated 1,300 FPCIW members use smartphones.[45] Iterative phases of product development require only five to seven representative users per prototype iteration,[46] justifying our sample size of 15 (five per app suite specialty feature).

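### The primary model includes between-feature interactions but does not name the pooled 45 vs 45 contrast, on which the 80% power rests, as the test of a feature

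*Combined protocol and SAP*

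**What the plan says.** Section II, A.2 (Clinical Trial Design Details) describes a fully crossed 2x2x2 design. Each feature is judged by "comparative assessments that involve 45 vs. 45 (feature present vs. absent) participants". The section adds that "it is incorrect to conceptualize this design as a test of outcome differences between eight separate inadequately powered cells" and that "the intent is to collapse information across cells so as to obtain a reasonably large sample size". It also says that the investigators will "downplay the importance of (though still include) significance testing of PA outcomes".

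Section III (Data Management, Analysis, & Statistical Considerations) sets out the analysis:

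- **Coding:** "Indicator variables will be created to code whether or not the participant had each of the specialty features installed on their phone". It notes that "The feature subgroups are not mutually exclusive since a participant can be randomized to receive 0, 1, 2, or all 3 of the features".
- **Primary model:** a mixed effects linear regression for change in daily steps, "adjusted for confounders (including presence/absence of other specialty features, between-feature interactions, select demographic variables", and also for baseline daily steps.
- **Power:** "the anticipated sample size (N=90) was chosen to enable 80% power", with an effect size of .45 and a one-tailed test at alpha .10.
- **Effect size:** a Cohen's d by presence vs absence of each feature, reported alongside the model.

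Section III does not give the order of the interactions, the numerical coding, or the coefficient or contrast that is the test of a feature.

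**The concern.** Interactions change the meaning of a feature's own coefficient. With 0/1 coding and no interactions, that coefficient is the pooled present-vs-absent effect. Once the feature's interactions are in the model, it is the effect among people who have neither of the other two features. If the three-way term is fitted as well, it is, before covariates, a comparison of two single cells of about 11 people each (90/8 = 11.25). That is the view of the design which Section II, A.2 rejects.

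Section III lists the interactions with the confounders, as adjustment terms. This makes it easier to read the feature's coefficient in the software output as its adjusted overall effect. An analyst who followed Section III literally could then report a different quantity from the one intended, with much less precision. It could disagree with the pooled Cohen's d for the same feature only because of the coding. Section II, A.2 itself warns against dropping features too early because of non-significant results.

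**Working it through.** **Inputs from the documents.** Analysed N = 90 (100 randomised, 10% attrition); 8 cells; effect size 0.45, read as a standardised difference in change in daily steps (SD = 1); one-tailed alpha .10 (z = 1.2816).

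**Assumptions.** No true interaction; near-equal cells; 0/1 indicators. The share of outcome variance explained by baseline steps and demographics (R2) is not given. It is taken as 0 first and then varied.

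**1. The plan's own figure.** For 45 vs 45:
- SE = sqrt(1/45 + 1/45) = sqrt(4/90) = 0.211.
- Normal approximation: power = Φ(0.45/0.211 − 1.2816) = 80.3%.
- Exact noncentral t on 88 df: 80.0%.

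The stated 80% is reproduced.

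**2. What the 0/1 coefficient estimates.** Let A be the feature's own 0/1 coefficient, and AB, AC and ABC its interaction coefficients. Averaging the feature's effect equally over the presence and absence of the other two gives

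marginal effect = A + 0.5·AB + 0.5·AC (+ 0.25·ABC if fitted).

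So A equals the marginal effect minus half of each two-way term (and minus a quarter of the three-way term). Any true two-way interaction moves A away from the pooled effect by half its size.

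**3. Variance in a balanced design.**
- Marginal contrast: 4/N, with two-way or with all interactions fitted.
- Own coefficient, two-way terms: 4/N + 0.25·(16/N) + 0.25·(16/N) = 12/N, which is 3 times.
- Own coefficient, three-way term added: a difference of two cell means, 2/(N/8) = 16/N, which is 4 times.

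**4. Power at N = 90, R2 = 0.** Ninety does not divide by 8. Cells of 11 were used, with one extra person in each of two complementary cells, over all four placements. Power is from the noncentral t.

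| Quantity tested | SE | Power |
|---|---|---|
| Marginal contrast, same model | 0.211 | 80.0% |
| Own 0/1 coefficient, two-way terms | 0.363-0.368 | 47-48% |
| Own 0/1 coefficient, three-way added | 0.417-0.426 | 41-42% |

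The normal approximation with exactly equal cells gives Φ(0.45/0.365 − 1.2816) = 48.0% and Φ(0.45/0.422 − 1.2816) = 41.5%.

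**5. Sensitivity to covariates.** With R2 up to 0.36 (correlation 0.6, assumed) and 8 covariate df (assumed), power rises to 91.5% for the marginal contrast. For the own coefficient it rises to 59-60% (two-way) or 51-52% (three-way). The 3- and 4-fold variance ratios do not depend on R2.

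**6. How often the two would disagree.** In 200,000 simulated draws at d = 0.45 and R2 = 0, for one cell placement:
- Two-way model: the marginal contrast was significant and the own coefficient was not in 35.0% of draws; the reverse occurred in 3.1%. Total 35.0 + 3.1, about 38%.
- Three-way model: 41.5 + 3.1, about 45%.

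**The case against.** Protocol and SAP are one document, and Section II, A.2 already states the target: 45 vs 45, collapsed over cells. An analyst would have to disregard it to report an effect with the other features absent. The 0/1 coding is inferred from the word indicator. The sentences around it concern pooled feature subgroups, and nothing says that a raw coefficient is the test. The low power figures therefore describe an analysis that the plan does not prescribe. Testing is also downplayed by design, no selection rule depends on one p-value, and the Cohen's d, the secondary-outcome t-tests and the usage and satisfaction t-tests do not use this model.

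Most of this stands, and it limits the severity. It does not remove the gap. Section II, A.2 gives an intent but no model term, and Section III, from which the analysis will be programmed, does not carry that intent into the model. The coding also changes the estimate, not only the p-value, so downplaying significance does not fully protect the primary result.

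A reader might go further and infer any of three things. None is supported:
- *The trial is underpowered, and needs the N of about 268 (two-way) or 358 (three-way) at which the own coefficient would reach 80%.* The 80% is correct for the intended contrast, which the same model can deliver at N = 90.
- *The interactions should be dropped.* In a balanced design they cost the marginal contrast essentially nothing.
- *The plan commits to the wrong coefficient.* It leaves the choice open.

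**Conclusion.** The point holds as a gap in specification, of minor to moderate weight. The plan states a pooled target and powers the trial correctly for it, but the primary model does not name the contrast that delivers it. If a feature's own 0/1 coefficient were reported, it would answer a different question whenever interactions exist. It would have 3 to 4 times the variance, and about 47-48% or 41-42% power in place of 80%.

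The variance ratios follow from the design with equal cells. The power figures also rest on an effect of 0.45 SD, no true interaction and no covariate gain. Blocking is not described. With simple randomisation to the eight cells, average power for the marginal contrast would be about 78%, so that assumption matters little here.

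**What to change.** In Section III, state that the primary test and estimate for each feature is the marginal present-vs-absent difference from the model, averaged with equal weights over the other two features, one-tailed at alpha .10. State whether two-way interactions only, or also the three-way term, are fitted.

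Either implementation works:
- Code each feature −0.5/+0.5 by randomised assignment. The coefficient is then the full present-vs-absent difference. With −1/+1 coding it is half the difference and must be doubled before it is reported.
- Keep 0/1 coding and test the contrast A + 0.5·AB + 0.5·AC (+ 0.25·ABC if fitted).

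Interaction estimates can still be reported, since the introductory text gives synergy between components as one reason for using MOST. The cost is one or two sentences in the SAP, with no extra data or participants and no change to N.
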